All patients who achieve systemic benefit (based on physician discretion) but later progress will be given the option of receiving reinduction. Optional radiation can be administered during reinduction. If administered, radiation will be given similar to what was done in the initial treatment. After the first round of reinduction, patients may receive additional reinduction if during their most recent post cycle 4 imaging disease control is observed without severe (grade >3) toxicity. Patients with either liver or lung lesions amenable to SBRT (either 50 Gy in 4 fractions or 60 Gy in 10 fraction) will be enrolled on this trial.

Treatment group 1) Ipilimumab + BMS-986156 (30 mg / 100 mg) x 4 for safety assessment (No SBRT) → Nivolumab x 26

Treatment group 2) Sequential (late SBRT) Ipilimumab + BMS-986156 (dose as determined in group 1) x 2 → SBRT → Ipilimumab + BMS-986156 (dose as determined in group 1) x 2 → Nivolumab x 26

Treatment group 3) Concurrent (early SBRT) Nivolumab (480 mg Q4W) + BMS-986156 (30mg) + SBRT → Nivolumab + BMS-986156 x 3 (30mg) → Nivolumab x 22

Group 1, 20 patients: Ipilimumab + BMS-986156 (30 or 100 mg) Dose Escalation → Nivolumab x 26 (up to 2 year maintenance)

Day 1 and every 21 days: Ipilimumab therapy at 3 mg/kg as a 90 minute intravenous (IV) dose and BMS-986156 at either 30 mg or 100 mg dose as a 60 min IV dose will be given in an outpatient setting. Dose cycles will be repeated every 21 days: on days 1, 22, 43, and 64 for a total of 4 cycles. Maintenance therapy of Nivolumab (480mg Q4W) will start day 85 and continue every 28 days, for 26 cycles.

A modified 3+3 dose escalation then expansion to a total of 10 patients per arm (escalation + expansion, if applicable) will be performed on two dose levels of this combination therapy. Details on de-escalation are presented under section 7.7.1.

Group 1

[figure not shown]

Diagram of Treatment Schedule for Ipilimumab + BMS-986156 (30 or 100 mg) Dose Escalation → Nivolumab x 26 (Treatment Group 1)

Group 2, 20 patients: Ipilimumab + BMS-986156 x 2 → SBRT → Ipilimumab + BMS-986156 x 2 → Nivolumab x 26 (up to 2 year maintenance)

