Day 1 and every 21 days: Ipilimumab therapy at 3 mg/kg as a 90 minute intravenous (IV) dose and BMS-986156 (dose as determined in group 1) as a 60 min IV will be given in an outpatient setting. Dose cycles will be repeated every 21 days: on days 1, 22, 43, and 64 for a total of 4 cycles. Nivolumab (480 mg Q4W) will start day 85 and continue every 28 days for 26 cycles. Enrollment of this group will start based on the following criteria. If 2 out of 6 patients, or less, display DLTs, then, enrollment of group 2 can begin. Alternatively, if 3 out of 6 patients, or more, display DLTs, then, enrollment of group 2 cannot begin until 10 patients have been treated in group 1.

SBRT: SBRT will be given after 2 doses of ipilimumab and BMS-986156 on days 29-32 for 50 Gy in 4 fractions or on days 29-40 for 60 Gy in 10 fractions (no SBRT during weekends): SBRT will be directed at 1-4 targetable liver or lung lesion(s). To minimize treatment breaks, patients may start radiation on a Monday.

Group 2

[figure not shown]

Diagram of Treatment Schedule for Ipilimumab + BMS-986156 x 2 → SBRT → Ipilimumab + BMS-986156 x 2 → Nivolumab x 26 (Treatment group 2).

Group 3, 20 patients: Nivolumab + BMS-986156 x 1 + SBRT → Nivolumab + BMS-986156 x 3 → Nivolumab x 22

First dose of Nivolumab + BMS-986156 and SBRT will be given concurrently (early) and followed by Nivolumab + BMS-986156 x 3; then, Nivolumab monotherapy for 22 cycles. Nivolumab will be administered for a total of 26 cycles, either as a combination or monotherapy, in this group. Enrollment of patients for this group will start around the same time as group 1. Choice of treatment group will be at the discretion of PI and treating physician.

Nivolumab therapy at 480 mg dose will be given on day 1 as a 30 minute IV dose and BMS-986156 at 30 mg dose will be given on day 1, 29, 57, 85 as a 60 min IV in an outpatient setting. Nivolumab monotherapy will start on day 113 and will continue for 22 cycles.

SBRT: SBRT will be given on days 1-4 (days 2-5 are acceptable if scheduling does not permit radiation to begin same day as infusions) for 50 Gy in 4 fractions or on days 1-12 for 60 Gy in 10 fractions (no SBRT during weekends). SBRT will be directed at 1-4 targetable liver or lung lesion(s). To minimize treatment breaks, patients may start radiation on a Monday.

Group 3

[figure not shown]

Diagram of Treatment Schedule for Nivolumab + BMS-986156 x 1 + SBRT → Nivolumab + BMS-986156 x 3 → Nivolumab x 22 (Treatment group 3)

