10.1. Data Set Descriptions

For group 1, after BMS-986156, dose as determined in group 1, an additional 4 patient expansion per dose level (10 patients total for each dose level) will be enrolled in that group, at the determined dose from group 1, to help determine biological endpoints. Should DLTs occur in more than 33% of patients enrolled into this expanded group, dosing at that level will be stopped. The next lower dose level will be considered the safe dose. A review of all DLTs observed will be conducted, and the need to lower the dose will be based on the discussion and agreement between the IRB and the Investigator.

All patients who receive any ipilimumab, BMS-986156, or nivolumab will be considered evaluable for toxicity.

For toxicity and response: all patients receiving at least 1 (concurrent group) or 2 (sequential group) treatment with trial drugs and completed half of the planned radiation treatment (except for group 1 where no radiation is given) will be considered evaluable for toxicity and response and included in the efficacy data set.

Group 1: (Total of 20 patients: 10 patients with 30 mg and 10 patients with 100 mg of BMS-986156, when combined with ipilimumab at 3mg/kg). Nivolumab (480mg) Q4W monotherapy will be administer for 26 cycles.

Group 2: 20 patients: trial drugs, two doses of ipilimumab (3mg/kg) combined with BMS-986156 (dose as determined in group 1) are given before SBRT. SBRT is given sequentially; followed by 2 more doses of ipilimumab + BMS-986156. Nivolumab (480mg) Q4W monotherapy will be administer for 26 cycles.

Group 3: 20 patients: First dose of trial drugs nivolumab (480 mg) and BMS-986156 (30 mg) are given concurrently with SBRT; followed by 3 doses of nivolumab (480 mg) and BMS-986156 (30 mg). Finally, Nivolumab as monotherapy for 22 cycles. Nivolumab will be administered for a total of 26 cycles in this group.

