10.2. Analysis

10.2.1. Statistical Analysis

Descriptive statistics will be computed for all relevant outcomes, including tumor response, and biomarker response. Descriptive analysis will include a global assessment of patient outcomes among all three groups. Group analysis will be conducted between groups. All patients receiving at least 1 (concurrent group) or 2 (sequential group) treatment with ipilimumab/Nivolumab/BMS-986156 and completed half of the planned radiation treatment (except for group 1 where no radiation is given) will be considered evaluable for toxicity and response and included in the analysis. Patients receiving any portion of the study drugs or interventions will be evaluable for toxicity.

Demographics, safety, and treatment efficacy will be compared in two separate analyses: (these tests are not for formal hypothesis testing, but for exploratory/descriptive purposes)

1. Among different treatment regimens: treatment group 1 vs. treatment group 2.
2. Among different treatment regimens: treatment group 2 vs. treatment group 3.
3. Among different SBRT targets liver vs lung: treatment group 2 vs. treatment group 3.

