10.2.4. Efficacy Analyses

Treatment success and clinical benefit will be defined as irCR or irPR or irSD, assessed using irRC (e.g. the best response obtained by a patient). Clinical benefit will be established as having irCR or irPR or irSD > 6 months. Measurements from all imaging, including those obtained during and after re-induction, will be considered in this analysis. Patients will be continuously evaluated for disease response via imaging until they are removed from the study. For secondary objectives a), b), and c), success probabilities will be estimated for each target separately (liver, lung) along with appropriate 95% confidence intervals. Safety comparisons among the groups will be assessed (primary end points) and efficacy comparisons between groups will be assessed with regard to the irRC outcomes while global, in-field irRC will be used for

hypothesis generating using Pearson chi-squared or Fisher exact tests. For secondary objective d) comparisons will be performed between group 2 and 3 as well as per treatment site (liver, or lung).

1. **Global irRC:** irRC that factors all lesions both index and non-index as outlined in 8.3.
2. **In-Field irRC:** irRC in which only SBRT-treated lesions will be considered and non-index lesions arising inside the SBRT PTV
3. **Out-Field irRC:** irRC in which only non SBRT-treated lesions will be considered and non-index lesions arising outside the SBRT PTV

For the secondary objective comparing the response between the arms. With 20 patients per arm, we would have 80% power using a two-sided 10% alpha with a chi-squared test to detect the following differences in response rates between treatment groups 44% vs 10%, 57% vs 20%, 68% vs 30% and 78% vs 40%. To increase statistical power, we may also combine the patients into a single dataset and fit a logistic regression model with response (CR+PR) as the outcome and SBRT dose, target (liver or lung) among other factors (including but not limited to: number of metastatic disease sites, number of prior treatments, primary cancer histology, age, pre-treatment KPS and Royal Marsden Score) as the predictors.

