Time-to-event analyses will be conducted via Kaplan-Meier analysis, with comparisons via the log-rank test made with regards to **overall survival**, with analysis beginning at receipt of the first SBRT fraction. At the discretion of the investigators, and if appropriate, a multivariate Cox regression will be done to adjust for (among other factors): number of metastatic disease sites, number of prior treatments, primary cancer histology, age, pre-treatment KPS and Royal Marsden Score.

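### Overall survival is timed from the first SBRT fraction, a date group 1 does not have in initial treatment and group 2 reaches about four weeks later than group 3; the plan should name the groups, the analysis set and a common start date

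*Combined protocol and SAP*

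**What the plan says.** The last paragraph of Section 10.2.4 is the only text on survival analysis. It plans Kaplan-Meier curves with log-rank comparisons of overall survival, "with analysis beginning at receipt of the first SBRT fraction", and an optional Cox model. It names neither the groups nor an analysis set.

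Elsewhere the combined protocol and SAP says:

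- **Group 1 treatment.** Section 1 gives ipilimumab plus BMS-986156 "x 4 for safety assessment (No SBRT"). Section 7.1 repeats this.
- **Efficacy set.** Section 10.1 requires one (concurrent) or two (sequential) drug treatments and half the planned radiation, with an exemption: "except for group 1 where no radiation is given) will be considered evaluable for toxicity and response and included in the efficacy data set". Section 10.2.1 repeats the rule. Neither mentions survival.
- **Comparisons.** Section 10.2.1 states "Demographics, safety, and treatment efficacy will be compared in two separate analyses". The first listed is "Among different treatment regimens: treatment group 1 vs. treatment group 2", followed by group 2 v group 3. It adds that "these tests are not for formal hypothesis testing, but for exploratory/descriptive purposes".
- **Timing of SBRT.** In group 2, "SBRT will be given after 2 doses of ipilimumab and BMS-986156 on days 29-32"; the ten-fraction schedule also starts on day 29. In group 3, SBRT starts on day 1, or day 2 where scheduling requires.

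**The concern.** A Kaplan-Meier curve, even a descriptive one, needs a start date for every patient it contains. The evaluability rule was adapted for a group without radiation, but the survival start date was not. A statistician following Section 10.2.4 literally must either leave group 1 out without being told to, or invent a start date for it.

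Restricting the analysis to groups 2 and 3 leaves a second, smaller problem. A group 2 patient must live and stay on study for about four weeks to reach the start of the clock, whereas a group 3 patient starts at once. Deaths, refusals and toxicity withdrawals in the first month therefore count in one group and not in the other. The half-of-radiation rule, if applied to survival, widens this difference.

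At stake are a defined survival time for each treated patient and an avoidable difference between two groups that the plan intends to compare. No dose decision, sample size or safety rule depends on it.

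**Working it through.** The plan gives no median, event count, hazard ratio or power for survival, so there is no figure of its own to reproduce.

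**1. Who lacks a start date.** Group 1 has 10 + 10 = 20 patients if both dose levels are expanded, out of a maximum of 60 (Section 10.2.5). Under Section 7.1.1.1 it is smaller if escalation stops early: 10 + 6 = 16 after 2 of 6 DLTs at level 2, 10 + 3 = 13 after 2 of 3 at level 2 with level 1 filled, and as few as 3 after 2 of 3 at level 1.

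Re-induction does not supply a usable date:
- The group 1 calendar allows it from 8 weeks after the last induction cycle: day 64 + 56 = day 120.
- It is for patients judged to have benefited, and radiation is optional (Section 7.1.2).
- The group 1 calendar note offers re-induction without mentioning radiation, and Section 7.1.2 also permits palliative or low-dose schedules, which need not be SBRT.

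**2. Offset between groups 2 and 3.** Nominally 29 − 1 = 28 days (27 if group 3 starts on day 2). With the ±3 day window in opposite directions it is 26 − 4 = 22 to 32 − (−2) = 34 days.

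**3. Effect of the offset.** Assumptions, none from the documents: identical true survival in both groups from first dose; Weibull, S(t) = exp[−ln 2 × (t/m)^k]; median m of 6, 8 or 12 months; shape k of 0.7 (falling hazard), 1.0 (constant) or 1.5 (rising); 24 months' follow-up from each group's clock start; 20 starting drug in each group. The delay is d = 28/30.4375 = 0.92 months.

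- Probability of death before the group 2 clock starts: p = 1 − S(d).
- Group 3 deaths: D3 = 20 × [1 − S(24)].
- Group 2 deaths: D2 = 20(1 − p) × [1 − S(24 + d)/S(d)].
- Apparent hazard ratio (HR), group 2 v 3: large-sample Cox estimate from these two curves.
- Standard error (SE) of log HR: √(1/D2 + 1/D3).

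Example, k = 0.7 and m = 6: p = 0.170, so 20 × 0.170 = 3.4 group 2 patients are lost before day 29. D3 = 16.8, D2 = 13.5, total 30.3. SE = √(1/13.5 + 1/16.8) = 0.365. HR = 0.88, and |log HR|/SE = 0.35.

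| Shape | p (m = 6 / 8 / 12) | Lost of 20 | HR | Deaths, both groups | SE of log HR | Shift in SEs |
|---|---|---|---|---|---|---|
| 0.7 | 0.170 / 0.141 / 0.108 | 3.4 / 2.8 / 2.2 | 0.88 / 0.89 / 0.90 | 30.3 / 28.4 / 25.1 | 0.365 / 0.377 / 0.401 | 0.35 / 0.32 / 0.27 |
| 1.0 | 0.101 / 0.077 / 0.052 | 2.0 / 1.5 / 1.0 | 1.00 / 1.00 / 1.00 | 35.6 / 33.7 / 29.2 | 0.336 / 0.345 / 0.370 | 0 / 0 / 0 |
| 1.5 | 0.041 / 0.027 / 0.015 | 0.8 / 0.5 / 0.3 | 1.13 / 1.10 / 1.08 | 39.1 / 38.5 / 34.4 | 0.320 / 0.323 / 0.341 | 0.38 / 0.30 / 0.22 |

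A 95% interval spans a factor of exp(1.96 × SE), 1.87 to 2.19 each way.

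**4. Sensitivity.** At 12 months' follow-up the HR runs from 0.85 to 1.15, at most 0.40 SE. At 36 months it runs from 0.89 to 1.13, at most 0.38 SE. A 4-month median with shape 1.5 gives 0.53 SE. Withdrawals before SBRT and the half-of-radiation rule are not modelled.

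**5. The evaluability rule and a day 1 start.** If survival ran from day 1 but the half-of-radiation rule still chose the patients, everyone in group 2 would have lived past day 29 by definition, and those days would be counted as survival. A day 1 start therefore needs that rule lifted for survival.

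**The case against.** The strongest reply is that a clock starting at SBRT naturally limits the curve to SBRT recipients. Section 10.2.1 lists group 2 v group 3, the trial's hypotheses concern SBRT, and Section 10.2.4 says "efficacy comparisons between groups will be assessed with regard to the irRC outcomes", which ties between-group efficacy to response rather than survival. On that reading no group 1 survival time is missing. This stands as a possible reading, but it is not stated, and the four-week stagger remains under it.

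Several stronger readings are tempting and the documents do not support them:

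- *That no analysis population exists.* Sections 10.1 and 10.2.1 define one. The gap is that they word it for toxicity and response and do not say whether it governs survival.
- *That a third of the trial is lost to the survival analysis.* This follows only if group 1 was meant to be included, and only if both its dose levels fill.
- *That the late start favours group 2.* The time before SBRT is not credited to group 2 when the clock starts at SBRT. The shift favours group 2 if hazard falls, vanishes if it is constant, and goes against group 2 if it rises. The documents give no survival data to choose between these.

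It can also be said that Section 10.2.5 counts 20 evaluable patients per group. If patients who die before SBRT are replaced, they fall outside the 20, and the losses above apply to those starting drug. This changes the standard errors only slightly.

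Finally, survival is absent from the objectives in Section 2, the comparisons are exploratory, and Section 1 assigns patients by disease status and discretion. All of this stands and limits the weight of the point.

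**Conclusion.** The point holds as a minor correction. Section 10.2.4 leaves open who is in the survival analysis and uses a start date that does not serve all three groups. If group 1 is included, up to 20 of 60 patients cannot be timed from initial treatment, and the survival part of group 1 v group 2 cannot be done as written. If it is not, the start is nominally 28 days later in group 2 (22 to 34 with the windows).

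The resulting group 2 v group 3 shift is of unknown direction and small against the precision of 20 per group: at most about 0.4 standard errors for assumed medians of 6 to 12 months, and about 0.5 with a 4-month median. These are maxima over an assumed grid of Weibull curves, not bounds from trial data. The case for change rests mainly on giving each treated patient a defined survival time, and less on bias.

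**What to change.** - In Section 10.2.4, measure overall survival from the first dose of study drug (day 1) in all patients who receive any dose, and name the groups the log-rank test compares.
- In Sections 10.1 and 10.2.1, state that the half-of-radiation evaluability rule applies to response and not to overall survival.
- Show any curve timed from SBRT only as a within-group landmark description for groups 2 and 3, with the number who died or left before SBRT.

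This costs a few sentences. The first-dose date exists for every treated patient, so no new data or procedures are needed. All planned patients then have a start date, and the offset between groups 2 and 3 becomes zero.

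Two limits remain. Patients withdrawn early under Section 7.3.5, including those who refuse SBRT, gain a start date but may be censored early and perhaps informatively, because no survival follow-up after withdrawal is described. A common start date also does not remove confounding from non-randomised assignment.

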10.2.5. Sample Size/Accrual Rate

The maximum planned number of evaluable patients will be 60, with 20 patients being treated in each group (groups: 1, 2 and 3). It is estimated that approximately 3 patients per month will be accrued and an approximate 4 week interval will be allowed between dose levels.

1. Physical exams and lab test measurements will be given a window of \pm 3 days unless patient/logistical/medical reasons intervene. Every patient requires physician evaluation within 7 days before start of study and \pm 3 days before each subsequent ipilimumab/BMS-986156 administration. Physical examination to include weight, vital signs, and performance status.
2. Initial tumor assessment should occur within 4-weeks before start of study and should be obtained via CT scans of the chest, abdomen and/or pelvis (contrast-enhanced preferred); MRI of the abdomen and pelvis; PET/CT scan (Preferred). If the aforementioned imaging modalities cannot be obtained an Ultrasound (US); or chest radiograph (least preferred) may be obtained.
3. Baseline visit within 2 weeks prior to initiation of therapy. Overlapping baseline tests can be combined with tests required for cycle 1 of ipilimumab/BMS-986156 administration as long as these baseline tests occur within 3 days before cycle 1.
4. First ipilimumab/BMS-986156 treatment will begin on day 1 (\pm 3) and start a 21 day/cycle combination therapy.
5. Nivolumab treatment will begin on day 85 (\pm 3) and start a 28 day/cycle combination therapy.
6. A baseline ECG will be recorded within 1-2-weeks (\pm 3 days) prior to therapy initiation
7. DLT assessment will include both evaluation by the phase I research nurse with optional input from the radiation oncology research nurses.
8. Mandatory blood and tissue biopsies samples will be obtained at baseline prior to the first cycle of ipilimumab/BMS-986156, at week 1 of cycle 2 (\pm 7 days) and at time of progression of disease.
9. Follow up appointments after last cycle of ipilimumab/BMS-986156 will occur in the Clinical Center for Targeted Therapy. Radiation oncology follow up visits will occur at the discretion of the treating radiation oncologist, recommended at 3 and 6 months.
10. Patients will be offered 4 cycles of reinduction ipilimumab/BMS-986156 if disease control (SD or PR) is observed at the first imaging after cycle 4 of ipilimumab. Reinduction can occur 8 weeks or later after the last cycle of ipilimumab/BMS-986156 induction. Patients can be offered repeat reinduction if disease control is observed and severe (grade >3 toxicity) is not observed.
11. Patients will receive routine scans to evaluate response by receiving either CT scans of the chest, abdomen, and/or pelvis (preferred); MRI of abdomen and pelvis; or PET/CT (preferred). After imaging performed for cycle 5, repeat imaging will be collected every 12 weeks (\pm 4 weeks) or sooner if clinically indicated by the discretion of PIs or treating physician.

Group 2: Ipilimumab + BMS-986156 x2 → SBRT → Ipilimumab + BMS-986156 x2 → Nivolumab x 26

Serum pregnancy test (women of childbearing potential) ¹	X ³																			
irRC imaging and tumor assessment	X ²														X ¹²					X ¹²
Biomarker studies	X ¹³					X ¹³										X ¹³				
Biopsies ⁹	X ⁹					X ⁹											X ⁹			

1. Physical exams and lab test measurements will be given a window of \pm 3 days unless patient/logistical/medical reasons intervene. Every patient requires physician evaluation within 7 days before start of study and \pm 3 days before each subsequent ipilimumab/BMS0986156 administration. Physical examination to include weight, vital signs, and performance status.
2. Initial tumor assessment should occur within 4-weeks before start of study and should be obtained via CT scans of the chest, abdomen and/or pelvis (contrast-enhanced preferred); MRI of the abdomen and pelvis; PET/CT scan (Preferred).If the aforementioned imaging modalities cannot be obtained an Ultrasound (US); or chest radiograph (least preferred) may be obtained.
3. Baseline visit within 2 weeks prior to initiation of therapy. Overlapping baseline tests can be combined with tests required for cycle 1 of ipilimumab/BMS-986156 administration as long as these baseline tests occur within 3 days before cycle 1.
4. SBRT will be given on days 29-32 (50Gy in 4 fractions) or day 29-40 (60Gy in 10 fractions).
5. First ipilimumab/BMS-986156 treatment will begin on day 1 (\pm 3) and start a 21 day/cycle combination therapy.
6. Nivolumab treatment will begin on day 85 (\pm 3) and start a 28 day/cycle combination therapy.
7. A baseline ECG will be recorded within 1-2-weeks (\pm 3 days) prior to therapy initiation
8. DLT assessment will include both evaluation by the phase I research nurse with optional input from the radiation oncology
9. Mandatory tissue biopsies will be obtained prior to the first cycle of ipilimumab/BMS-986156,at the end of the cycle 2, and at progression of disease as determined per the discretion of the treating physician and/or study PIs.
10. Follow up appointments after last cycle of ipilimumab/BMS-986156 will occur in the Clinical Center for Targeted Therapy. Radiation oncology follow up visits will occur at the discretion of the treating radiation oncologist, we recommend at 3 and 6 months.
11. Patients will be offered 4 cycles of reinduction ipilimumab/BMS-986156 +/- radiation if disease control (SD or PR) is observed at the first imaging after cycle 4 of ipilimumab/BMS-986156. Reinduction can occur 8 weeks or later after the last cycle of ipilimumab/BMS-986156 induction. Patients can be offered repeat reinduction if disease control is observed and severe (grade >3 toxicity) is not observed.
12. Patients will receive routine scans to evaluate response by receiving either CT scans of the chest, abdomen, and/or pelvis (preferred); MRI of abdomen and pelvis; or PET/CT (preferred).
13. Mandatory blood will be obtained prior to the first cycle of ipilimumab/BMS-986156, on the last day of radiation treatment (Day 32/33 for patients receiving 50 Gy in 4 fractions or on day 40 for patients receiving 60 Gy in 10 fractions), and at progression of disease determined by the discretion of the treating physician and/or study PIs.

Group 3: Concurrent Nivolumab + BMS-986156 + SBRT → Nivolumab + BMS-986156 x3 → Nivolumab x 22

Assessment Tool (Study related visit range \pm 3 days)	Baseline ³	Cycle 1		Cycle 2		Cycle 3		Cycles 4		Cycles 5-26		Follow Up Period (1 year) Every 2-4 months +1 month ¹⁰	
		Week		Week		Week		Week		Week			
		1	2	1	4	1	4	1	4	1	4		
SBRT simulation (4DCT performed within 3 weeks prior to SBRT treatment)	X												
SBRT		X ⁴										X ¹³	
Nivolumab		X ⁵		X ⁵		X ⁵		X ⁵		X ⁵		X ¹³	
BMS-986156		X ⁵		X ⁵		X ⁵		X ⁵				X ¹³	
DLT Assessment ⁸				X ⁸									
History & Physical Exam (including weight measurement) ¹	X ^{1,3}	X		X		X		X		X		X ¹⁰	
CBC & differential ¹	X ^{1,3}	X		X		X		X				X ¹⁰	
ECG ⁷	X ^{3,7}												
Sodium, potassium, chloride, bicarbonate, BUN, creatinine, glucose, calcium, magnesium, phosphorus, albumin, total protein, alkaline phosphatase, total bilirubin, uric acid, SGOT (AST), SGPT[ALT], TSH ¹	X ^{1,3}	X ¹		X ¹		X ¹		X ¹		X ¹		X ¹⁰	
Urinalysis ¹	X ^{1,3}												
Hepatitis B/C & HIV screening	X ^{1,3}												
Serum pregnancy test (women of childbearing potential) ¹	X ^{1,3}												
irRC imaging and tumor assessment ²	X ²					X ¹¹				X ¹¹		X ^{10,11}	
Biomarker studies	X ¹²		X ¹ 2								X ¹²		

Biopsies⁹	X⁹		X⁹						X⁹
-----------------------------	----------------------	--	----------------------	--	--	--	--	--	----------------------

1. Physical exams and lab test measurements will be given a window of \pm 3 days unless patient/logistical/medical reasons intervene. Every patient requires physician evaluation within 7 days before start of study and \pm 3 days before each subsequent nivolumab/BMS-986156 administration. Physical examination to include weight, vital signs, and performance status.
2. Initial tumor assessment should occur within 4-weeks before start of study and should be obtained via CT scans of the chest, abdomen and/or pelvis (contrast-enhanced preferred); MRI of the abdomen and pelvis; PET/CT scan (Preferred). If the aforementioned imaging modalities cannot be obtained an Ultrasound (US); or chest radiograph (least preferred) may be obtained.
3. Baseline visit within 2 weeks prior to initiation of therapy. Overlapping baseline tests can be combined with tests required for cycle 1 of nivolumab/BMS-986156 administration as long as these baseline tests occur within 3 days before cycle 1.
4. SBRT will be given on days 1-4 or 2-5 (50Gy in 4 fractions) or 1-12 (60Gy in 10 fractions) of treatment protocol.
5. First nivolumab/BMS-986156 treatment will begin on day 1 (\pm 3) and start a 28 day/cycle combination therapy for 4 cycles total.
6. Nivolumab monotherapy will start on cycle 5 and end cycle 26. Nivolumab will be administered for 22 cycles as monotherapy for a total of up to 26 cycles.
7. A baseline ECG will be recorded within 1-2-weeks (\pm 3 days) prior to therapy initiation
8. DLT assessment will include both evaluation by the phase I research nurse with optional input from the radiation oncology research nurses.
9. Mandatory tissue biopsies samples will be obtained at baseline prior to the first cycle of nivolumab/BMS-986156, after cycle 2 infusion (week 1 of cycle 2), and at time of progression of disease.
10. Follow up appointments after last cycle of nivolumab will occur in the Clinical Center for Targeted Therapy. Radiation oncology follow up visits will occur at the discretion of the treating radiation oncologist, recommended at 3 and 6 months.
11. Patients will receive routine scans to evaluate response by receiving either CT scans of the chest, abdomen, and/or pelvis (preferred); MRI of abdomen and pelvis; or PET/CT (preferred). Routine scans will be performed every 12 weeks (\pm 4 weeks or sooner if clinically indicated per the discretion of the treating physician or study PIs).
12. Mandatory blood samples will be obtained at baseline prior to the first cycle of nivolumab/BMS-986156, on the last day of radiation treatment (day 4/5 of cycle 1 for patients receiving 50 Gy in 4 fractions or day 12 of cycle 1 for patients receiving 60 Gy in 10 fractions), and at progression of disease determined by the discretion of treating physician and/or study PIs.
13. Patients will be offered 4 cycles of reinduction nivolumab/BMS-986156 +/- radiation if disease control (SD or PR) is observed at the first imaging after cycle 4 of ipilimumab/BMS-986156. Reinduction can occur 8 weeks or later after the last cycle of nivolumab/BMS-986156 induction. Patients can be offered repeat reinduction if disease control is observed and severe (grade >3 toxicity) is not observed

